5.3 Dietary restrictions and smoking

5.3.1 Part A

No use of > 5 cigarettes per day or equivalent use of tobacco products is allowed during the study until V399.

5.3.2 Part B

No use of > 10 cigarettes per day or equivalent use of tobacco products is allowed during the study until EOS.

5.4 Other restrictions

During 48 hours post injection, subjects should consider only modest exertion of the concerned knee joint and/or leg.

No high-impact physical exercise (e.g. football, basketball, running, contact sports) is allowed from Day 1 until EoS.

Non-drug treatments (e.g. physiotherapy) must be reported in the Concomitant medications/Significant non-drug therapies CRF. Further recommendations are given in the SOM.

6 Treatment

6.1 Study treatment

Details on the requirements for storage and management of study treatment, and instructions to be followed for subject numbering, prescribing/dispensing and taking study treatment are outlined in the SOM.

6.1.1 Investigational treatment and control drugs

Table 6-1 Overview of study medication

Study drug name	Formulation	Unit dose	Packaging	Provided by
LNA043	Lyophilisate in Vial (LYO)	10mg	Open label bulk supply	Novartis
Placebo to LNA043	Lyophilisate in Vial (LYO)	0mg	Open label bulk supply	Novartis

6.1.2 Additional study treatment

No additional treatment beyond investigational drug and control drug are included in this trial.

6.2 Treatment arms

6.2.1 Part A

Subjects will be assigned to one of the following two treatment arms in a ratio of "3:1" Study treatments are defined as:

- A: single i.a. injection of 20 mg LNA043, Commercially Confidential Information
- B: single i.a. injection of placebo to 20 mg LNA043, CCI

6.2.2 Part B

Subjects will be assigned to one of the following three treatment arms in a ratio of "1:1:1" Study treatments are defined as:

•	A: single i.a. injection of 20 mg LNA043,	Commercially Confidential Information
•	B: single i.a. injection of 40 mg LNA043,	Commercially Confidential Information
•	C: single i.a. injection of placebo	Commercially Confidential Information

6.3 Treatment assignment and randomization

After eligibility confirmation, at the first dosing visit (Day 1) (or one day before), subjects will be randomized via Novartis Interactive Response Technology (NIRT) to one of the two (Part A) or three (Part B) treatment arms. The investigator or his/her delegate will log in the NIRT system after confirming that the patient fulfills all the inclusion/exclusion criteria. The NIRT will assign a treatment arm to the patient. The treatment arm information will not be communicated to the caller (investigator or his/her delegate).

Follow the details outlined in the SOM regarding the process and timing of treatment assignment and randomization of subjects.

The investigator will enter the screening number in the eCRF.

Randomization will be stratified by type of lesion (femoral condyle or patella) only in Part A. Randomization will not be stratified in Part B.

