- PART A ONLY: Patient has an onset of pain and impairment of function between two (2) months and two (2) years before screening.
- Commercially Confidential Information
- Part B ONLY: Diagnosis of femorotibial OA in the target knee
- Part B ONLY: K&L grade 2 or 3 OA of the knee with minimum Joint Space Width (JSW) 2.00-4.00 mm at screening
- Part B ONLY: History of pain due to OA in the target knee for at least 6 months at screening

Key Exclusion criteria

- Women of child-bearing potential, defined as all women physiologically capable of becoming pregnant, unless they are using highly effective methods of contraception during dosing and for 15 days after stopping of investigational drug.
- Part A: Regular smokers (> 5 cigarettes/day). Urine cotinine levels will be measured during screening for all patients. Regular smokers will be defined as any patient who reports tobacco use of > 5 cigarettes/day and/or who has a urine cotinine ≥ 500 ng/mL.

Part B: Regular smokers (> 10 cigarettes/day).

- PART A ONLY: Patient has radiologically apparent degenerative joint disease in the target knee as determined by Kellgren and Lawrence grade ≥2 based on X-ray evaluation performed within 9 months from screening.
- Patient has had surgical treatment of the target knee using mosaicplasty, microfracture, meniscectomy >50%
 - (Note: prior diagnostic arthroscopy with debridement and lavage, <50% meniscectomy, lateral release, patellar realignment, medial patellofemoral ligament reconstruction are acceptable if performed at least 2 months prior to screening; anterior cruciate ligament reconstruction is acceptable if performed 12 months prior to screening, or less if restoration of joint function is evident, and agreed by the sponsor).
- Patient has an unstable target knee joint (including but not limited to posttraumatic or congenital laxity) or insufficiently reconstructed ligaments based on medical history and physical examination by the investigator.
- PART A ONLY: Patient has patellofemoral dysplasia Dejour Grade B-D based on X-ray or MRI evaluation
- Patient has malalignment (valgus- or varus-deformity) in the target knee
 ≥ 5° (Part A) or > 7.5° (Part B) based on X-ray evaluation at screening.
 In suspected cases, the mechanical axis must be established
 radiographically through complete leg imaging during standing and in
 postero-anterior (PA) projection.

	Part B ONLY: Clinical signs of inflammation in the target knee		

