3.1.2 Part B

This is a non-confirmatory, randomized, placebo-controlled, patient and investigator blinded study in patients with K&L 2-3 knee OA.

Commercially Confidential Information

Following their informed consent, patients will be assessed for eligibility at the screening visit. Investigators may perform an unscheduled visit between Screening and first treatment on Day 1 if deemed to confirm eligibility of the subject, or verify safety.

Screening X-ray will be evaluated by the central reader for eligibility. Baseline MRI will be performed after eligibility has been verified. On Day 1, eligible patients will receive a CCI i.a. injection of either LNA043 20 mg, LNA043 40 mg, or matching placebo according to a 1:1:1 randomization ratio. Commercially Confidential Information

During the treatment period, safety and pharmacokinetics will be assessed as detailed in the Assessment schedule (Table 8-2). Patients will be monitored on site 3 hours after the i.a. injections. The investigator will schedule telephone calls with the patient approximately 48 hours after each study drug administration for follow-up assessment of safety. In case of safety concerns, the patient will return to the clinical site for assessment and follow-up.

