3.2.2 Part B

- Based on the positive results of the CLNA043X2201 study and of this ongoing CLNA043X2202 study (Part A), a broader patient population of knee OA with high medical need patient population is now being evaluated in part B.
- The patient population of knee OA K&L 2-3 with JSW 2.00-4.00mm has been selected based on the post-hoc analysis of the FORWARD trial (Gühring et al 2019),

- The MRI data collected at different time points will allow for the evaluation of the short-and long-term effect of one monthly cycle of i.a. treatment with LNA043 and a comparison between the 2 doses tested (20 mg and 40 mg). Meanwhile, since the image analysis will cover well-defined regions the articular cartilage throughout the knee as has been done in part A, results from part B, especially those obtained from the 20 mg group, may also be compared with the results from part A to evaluate the potential added benefit of the monthly dosing regimen in the index region (as defined in part B) vs the damaged region (as defined in part A).
- The monthly dosing regimen (x 4) has been selected based on the results of the FIH clinical study, which suggests a long PD effect of LNA043.

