In Part A, the study population will be comprised of male and female patients with partial thickness cartilage lesions of one knee. A total of approximately 60 patients will be enrolled in the study and randomized. Randomization will be stratified by type of lesion (femoral condyle or patella). At least 48 patients are expected to complete the study (20% drop out rate). Additional patients may be enrolled if the dropout rate will exceed 20%.

The investigator must ensure that all patients included in the study meet the eligibility criteria. No additional criteria should be applied by the investigator, in order that the study population will be representative of all eligible patients. Patient selection is to be established by checking through all eligibility criteria at screening and before dosing. A relevant record (e.g. checklist) of the eligibility criteria must be stored with the source documentation at the study site.

Deviation from any entry criterion excludes a patient from enrollment into the study.

Commercially Confidential Information

Part B

In Part B, the study population will be comprised of male and female patients with knee OA (K&L 2-3). A total of approximately 75 patients will be enrolled in the study and randomized. At least 69 patients are expected to complete the study (10% drop out rate). Additional patients may be enrolled if the dropout rate will exceed 10%. The investigator must ensure that all patients included in the study meet the eligibility criteria. No additional criteria should be applied by the investigator, in order that the study population will be representative of all eligible patients. Patient selection is to be established by checking through all eligibility criteria at screening and before dosing. A relevant record (e.g. checklist) of the eligibility criteria must be stored with the source documentation at the study site.

In total, 135 patients are expected to be randomized into the study.

Deviation from any entry criterion excludes a patient from enrollment into the study.

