11.4.2.2 Part B

The primary efficacy variable, change from baseline in cartilage volume/thickness in the index region, assessed based on MRI at Weeks 28 and 52. will be analyzed using a mixed model repeated measures (MMRM), including baseline and all time points to compare treatment groups at Week 28 and Week 52. The model will include baseline measure, treatment, timepoint, treatment*timepoint as fixed effects, participant as a random effect. 90% two-sided confidence intervals for the treatment effect will be formed at Weeks 28 and 52. If deemed appropriate, the endpoint measure data will be transformed to facilitate analysis. Considering that the time course of response to LNA043 is not known, statistically significant differences between active drug (either LNA043 dose) and placebo at either Week 28 or Week 52 will be considered as a positive result.

The safety variables will be summarized descriptively by treatment group for part A and part B.

Exploratory variables will be summarized descriptively by treatment group and associations with primary and secondary variables will be explored.

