6.1.3.2 Part B

The primary efficacy variable for Part B, change from baseline in cartilage volume in the index region will be analyzed using a mixed effect model for repeated measures (MMRM) analysis of variance model, including all-time points to compare treatment groups at Weeks 28 and 52. The model will include baseline as a covariate, treatment, timepoint, treatment*timepoint as fixed effects. An unstructured covariance will be assumed; if not possible, other appropriate covariance structures will be explored such as Autoregressive (AR(1)), Compound symmetry, etc.

The change from baseline in cartilage thickness in the index region will be similarly analyzed using the MMRM described above for the change from baseline in cartilage volume in the index region.

A two-sided 90% confidence intervals for the treatment effect will be formed at Weeks 28 and 52. Considering that the time course of response to LNA043 is not known, statistically significant differences (one-sided p-value of treatment superiority to placebo at 95% significance level) between active drug (either LNA043 dose) and placebo at either Week 28 or Week 52 will be considered as a positive result. No multiplicity adjustment will be considered. If deemed appropriate, the endpoint measure data will be transformed to facilitate analysis.

Same analyses (table and figures) for the MMRM models of change from baseline in cartilage volume in the index region as well as for the change from baseline in the cartilage thickness in the index region may be implemented based on the Population A, defined in Section 6.

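### Part B is unstratified with about 25 patients per arm, and its visible MMRMs adjust only for baseline MRI, leaving out K&L grade and joint space width: a valid plan that gives up a cheap safeguard

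*Protocol*

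**What the plan says.** **Allocation.** On size, Protocol section 4 (Population, Part B) says: "A total of approximately 75 patients will be enrolled in the study and randomized". It expects at least 69 to complete. Protocol 3.1.2 allocates them "according to a 1:1:1 randomization ratio". Protocol 6.3 stratifies Part A by lesion type, then adds: "Randomization will not be stratified in Part B".

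**Models.** For the Part B primary endpoint, Protocol 11.4.2.2 states: "The model will include baseline measure, treatment, timepoint, treatment*timepoint as fixed effects, participant as a random effect". SAP 6.1.3.2 has the same fixed part: "The model will include baseline as a covariate, treatment, timepoint, treatment*timepoint as fixed effects". It uses this model for volume and for thickness. Protocol 11.7 and SAP 6.2.3.2 give a corresponding model for the secondary T2 endpoint. None of these lists K&L grade or JSW.

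**The omitted variables.** The synopsis requires "K&L grade 2 or 3 OA of the knee with minimum Joint Space Width (JSW) 2.00-4.00 mm at screening". Protocol 8.4 has every Part B subject X-rayed at screening, and Protocol 3.1.2 has the film read centrally. On the choice of population, Protocol 3.2.2 says: "The patient population of knee OA K&L 2-3 with JSW 2.00-4.00mm has been selected". It bases that choice on a post-hoc analysis of an earlier trial of another compound.

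**Decision rule.** Under SAP 6.1.3.2, a one-sided 5% result for either dose at Week 28 or Week 52 counts as positive, with no multiplicity adjustment.

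**The concern.** The endpoint is change in cartilage over 28 and 52 weeks. Baseline volume or thickness records how much cartilage is present, which need not capture how fast it is being lost. K&L grade and JSW are the severity measures by which the sponsor defined this population, and the title of the cited post-hoc analysis refers to patients at risk of progression. It is therefore reasonable to suspect that they carry information about change.

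With small unstratified arms, severity can differ by chance. A model without severity terms may then credit the difference to the drug or let it mask a drug effect. Both doses share one placebo arm, so an atypical placebo arm moves both contrasts the same way. If the covariates are prognostic, leaving them out also widens the 90% intervals on which the decision rests. Part A handles its main disease feature differently: lesion type is a stratification factor and also a model term.

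**Working it through.** **Inputs from the documents.** 75 randomised 1:1:1 gives 75/3 = 25 per arm; 69 completers give 69/3 = 23 per arm. On the plan's own figures, 75 × 0.9 = 67.5 against 69 stated, and 69/0.9 = 76.7 against 75; these agree within two patients. The Part B effect size, SD and power are redacted, so power for the actual design cannot be reproduced.

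**Assumptions, not in the documents.** Grade 3 prevalence p of 30% to 50%; a grade effect g in SD units beyond baseline MRI; and R², the share of residual variance that the two covariates explain beyond baseline MRI.

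**1. Chance imbalance.** Grade 3 counts per arm are Binomial(25, p). A gap of 20 points is 5 patients.

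| | p = 0.5 | p = 0.3 |
|---|---|---|
| One dose vs placebo, gap ≥ 20 points | 20% | 16% |
| At least one of two doses vs placebo | 34% | 28% |

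These count both directions. In one given direction, such as favouring active, the chances are about half: 10% and 8% per contrast, 17% and 14% for at least one dose. With 23 per arm, where a 20-point gap also takes 5 patients, the two-directional figures are 18% and 15% per contrast, 31% and 25% for at least one dose.

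**2. Effect of a 20-point imbalance.** The SE of a contrast in SD units is sqrt(2/25) = 0.283. The shift is 0.2 × g:

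- g = 0.25: 0.05 SD = 0.18 SE
- g = 0.5: 0.10 SD = 0.35 SE
- g = 1.0: 0.20 SD = 0.71 SE

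For g = 0.5 favouring active, conditional one-sided error is 1 − Φ(1.645 − 0.354) = 9.8%. Removing the grade variance (0.25 × 0.5² = 0.0625) from the conditional spread gives 1 − Φ(1.291/sqrt(0.9375)) = 9.1%. So it is 9% to 10% instead of 5%. In the opposite direction the same shift hides an effect. Averaged over all randomisations the error remains 5% per comparison.

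**3. Precision gained by adjusting.** Ignoring the cost of estimation, the SE factor is sqrt(1 − R²). Charging two degrees of freedom at N = 75, it is sqrt[(1 − R²)(1 + 2/68)].

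| R² | Ignoring df | Net of 2 df | Net change in SE | Patients equivalent |
|---|---|---|---|---|
| 0.02 | 0.990 | 1.004 | about 0% | −1% |
| 0.05 | 0.975 | 0.989 | −1% | +2% |
| 0.10 | 0.949 | 0.963 | −4% | +8% |
| 0.20 | 0.894 | 0.907 | −9% | +21% |

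Break-even is R² = 1 − 1/(1 + 2/68) = 0.029. If the covariates explained nothing, the SE would rise by sqrt(1 + 2/68) − 1 = 1.5%.

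**4. In power terms.** Take a reference design with 80% power by the normal formula at 25 per arm: d = (1.645 + 0.842) × 0.283 = 0.70, or 79.3% by the t-distribution. Adjusted t-based power is 79.0%, 80.1%, 81.9% and 85.7% at R² = 0.02, 0.05, 0.10 and 0.20.

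**The case against.** The strongest reply is that nothing here is an error. Unstratified randomisation with baseline adjustment is valid, Part B is declared non-confirmatory, and the covariate already in the model measures the same tissue as the endpoint. That stands. A reader might infer that the Part B comparison is biased or its error rate inflated. The documents do not support this: the inflation in step 2 is conditional on one imbalance in one direction.

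A reader might also infer that the sponsor treats grade and JSW as established predictors of cartilage loss. Protocol 3.2.2 says only that a post-hoc analysis guided the choice of population, and the at-risk wording comes from a reference title. Choosing patients at risk does not show that grade 2 versus 3, or JSW within a 2 mm window, predicts change inside that group. JSW may also overlap with baseline thickness. The prognostic strength is therefore an assumption, and the gain could be nil.

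The assumptions also need to be kept consistent: a 0.5 SD grade effect at 50% prevalence implies that grade explains about 6% of variance, so the 0.35 SE shift should not be paired with the 20% row of the precision table.

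Finally, redaction limits the claim. SAP 6.1.4 (supportive analysis) is blacked out and could contain an adjusted analysis. The list of baseline CRF items in Protocol 8.4 is partly redacted, so the X-rays are certain but entry of both values in the analysis database is not. One cannot say that severity is adjusted for nowhere, only that the visible primary and secondary models omit it.

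**Conclusion.** The point holds as a cheap improvement to a valid plan. The visible Part B models leave out two severity measures read at screening in every patient, and no stratification guards against imbalance in them. A 20-point imbalance in grade is not rare: 16% to 20% per contrast and 28% to 34% for at least one dose, in either direction, at 30% to 50% grade 3. Its consequence is moderate under a 0.5 SD grade effect: 0.35 SE, and conditional one-sided error of about 10% if it favours active. The precision gain runs from nothing to about 9% of the SE for R² between 0.02 and 0.20. Prevalence, grade effect and R² are all assumed; the documents give none of them. The case rests on low cost against a plausible but unproven benefit.

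**What to change.** Before database lock, and without reference to treatment-arm data, add to the Part B MMRMs in SAP 6.1.3.2 and 6.2.3.2:

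- screening K&L grade (2 vs 3) as a fixed effect;
- screening minimum JSW as a continuous covariate;
- covariate-by-timepoint terms, if the intention is to allow for different rates of loss at Weeks 28 and 52.

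Keep the baseline-only model as a sensitivity analysis and tabulate both variables by arm. Align Protocol 11.4.2.2 and 11.7, or record the departure from them in the SAP. Confirm that both values are in the analysis database.

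Fixing the choice blind to arm data matters because Protocol Table 6-2 lets statisticians and programmers be unblinded at patient level from randomisation onward. Covariates added after an imbalance has been seen would look data-driven.

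Randomisation and visits do not change. The cost is wording plus about two degrees of freedom (more with timepoint terms), and a negligible SE loss, at most about 1.5%, if the covariates explain less than about 3% of residual variance.

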6.4 Treatment blinding

This is a subject and investigator-blinded study. Subjects and investigators will remain blinded to study treatment throughout the study, except where indicated below.

The identity of the treatments will be concealed by the use of study drugs that are all identical in packaging, labeling, schedule of administration, appearance, and odor.

Site staff

With the exception of any unblinded site staff identified below, all site staff (including study investigator and study nurse) will be blinded to study treatment throughout the study.

Unblinding a single subject at site for safety reasons (necessary for subject management) will occur via an emergency system in place at the site (see Section 6.7).

Drug product will be supplied in bulk, so an unblinded pharmacist or delegate who is independent of the study team will be required in order to maintain the blind. After blinded investigator or his/her delegate performs the randomization in NIRT system, the unblinded pharmacist will log into the NIRT system and see the treatment arm assigned to the randomized subject. Appropriate measures must be taken by the unblinded pharmacist to ensure that the treatment assignments are concealed from the rest of the blinded site staff.

Sponsor staff

The following unblinded sponsor roles are required for this study.
Unblinded field monitor(s)
Unblinded clinical staff managing drug re-supply to site
Unblinded sample analyst(s) (PK blood)

Commercially Confidential Information

The unblinded field monitors are required to review drug accountability and allocation at site. The unblinded monitors will be unblinded through unblinded user access to the NIRT system and review of source documentation compiled by the unblinded pharmacist or delegate, which details treatment allocation to individual subjects. The names of the unblinded monitor(s) are detailed in the Monitoring Plan.

The sample analysts will receive a copy of the randomization schedule (via request to the Randomization Office), to facilitate analysis of the samples. The sample analysts will provide the sample data to the study team under blinded conditions unless otherwise allowed.

Study programmers and other personnel involved in study data analysis (e.g. CCI) are allowed to access treatment assignment information for the purpose of conducting interim analyses.

The clinical trial team is allowed to share unblinded results with other sponsor staff (e.g. decision boards) as required for internal decision making on the study or the project at the time of interim analyses while the study is ongoing.

All unblinded personnel will otherwise keep randomization lists and data or information that could unblind other study team members confidential and secure except as described above.

Following final database lock all roles may be considered unblinded.

Table 6-2 Blinding Levels (Part A and B)

	Time or Event			
Role	NIRT set-up & go-live	Randomization & treatment arm assignment & dosing	Safety event (single subject unblinded)	Interim analysis
Subjects/Patients	В	В	UI	В
Site staff	В	В	UI	В
Unblinded site staff (see text for details)	В	UI	UI	UI
Drug Supply and Randomization Office	UI	UI	UI	UI
Unblinded sponsor staff (see text for details)	В	UI	UI	UI
Statistician/statistical programmer/data analysts	В	UI	UI	UI
Independent committees used for assessing interim results	NA	NA	NA	NA
All other sponsor staff not identified above	В	В	UI	B*

B Remains blinded

B* blinded at individual level

NA Not applicable

UI Allowed to be unblinded on individual patient level

